The sample size estimation is based on the primary outcome, running-related pain. Lopes et al. [9] reported a median pain level of 3 (IQR: 2-5) among 1049 recreational runners. We expect similar pain levels at baseline which, if normally distributed, should result in a mean pain of 3 and a standard deviation of 2.22 ($SD \approx IQR/1.35$). We forecast a 40% reduction in running-related pain in the intervention group over the course of the trial (from baseline to follow-up). Using the formula $n = (Z_{\alpha/2} + Z_{\beta})^2 * 2\sigma^2/d^2$, where d is the expected difference between groups, to detect a 40% reduction in pain (1.2 units) with 80% power at a 5% significance level, we initially require 70 participants per group [50]. Factoring in an anticipated 15% dropout, this number increases to 82 participants per group. To accommodate the pre-planned secondary subgroup analyses in the future, we further inflate the number by approximately 20%, leading to a total of 100 participants in each group. Hence, this study aims to recruit a cumulative sample size of 200 participants.

Recruitment

Participants are primarily targeted and approached within the local London parkrun communities. Following their routine Saturday 5-km run, a strategic engagement occurs where they will be approached by study representatives. The parkrun offers a natural setting to converse with potential participants who are already involved in regular running activities. During this engagement, participants are presented with an oral briefing about the study, its objectives, and the potential benefits of their participation. This method not only taps into a pool of runners but also allows for immediate interaction, answering any initial queries they might have. Interested runners, eager to contribute or benefit from the study, are subsequently invited to the Biomechanics Laboratory of the Faculty of Sport, Technology, and Health Sciences at St Mary's University in Twickenham, London, UK. Here, they are introduced to

the broader scope of the study, the commitment expected from them, and the potential implications of the research, and ultimately a formal enrolment into the study.

Allocation

Upon completion of the baseline questionnaires, participants will be equally distributed (1:1 ratio) to the two comparison groups (intervention group and “do-as-usual” control group) using a balanced block randomisation method.

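### The printed sample-size formula and inputs give 54 per group, not 70, and the difference entered is a within-arm change that equals the between-group difference only if controls do not change

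*Combined protocol and SAP*

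**What the plan says.** The Sample size section starts from a survey that "reported a median pain level of 3 (IQR: 2-5) among 1049 recreational runners". It assumes similar baseline pain, which "should result in a mean pain of 3 and a standard deviation of 2.22". On the effect it says: "We forecast a 40% reduction in running-related pain in the intervention group over the course of the trial", measured from baseline to follow-up.

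It then gives the usual normal-approximation formula for two means, n = (z_α/2 + z_β)² × 2σ²/d². It defines d as the expected between-group difference and concludes: "to detect a 40% reduction in pain (1.2 units) with 80% power at a 5% significance level, we initially require 70 participants per group". For 15% dropout, "this number increases to 82 participants per group". A further allowance of about 20% for later subgroup analyses brings the target to 100 per group, 200 in all.

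The Primary outcome section defines the contrast to be tested as the between-arm difference in mean change in running-related pain, adjusted for baseline. The section on the control group lets controls manage their pain however they like, short of using the study insoles.

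**The concern.** There are two separate problems.

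- **The arithmetic.** The formula and every input are printed, so the result can be recomputed, and it is not 70. The dropout and subgroup steps start from 70 and inherit the discrepancy. The 80% power attached to 70 is therefore not the power of that design.
- **The meaning of d.** The formula needs a difference between arms. The number supplied, 40% of a mean of 3, is a forecast change inside one arm. The two are equal only if mean control-arm pain stays where it started. The section does not state that assumption, and controls are free to treat their pain.

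The problems pull in opposite directions. The first leaves the trial with more power than claimed for a difference of 1.2. The second means that the difference actually tested may be smaller than 1.2. A reader of a null result who relies on 80% power for 1.2 would be misled either way.

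**Working it through.** **Inputs, all from the Sample size section**

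- SD: IQR width 5 − 2 = 3, and 3/1.35 = 2.22.
- d: 40% × 3 = 1.2.
- Two-sided 5% (the formula uses z_α/2), z = 1.960.
- 80% power, z = 0.842.

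**Trying to reproduce 70**

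n = (1.960 + 0.842)² × 2 × 2.22² / 1.2² = 7.849 × 9.857 / 1.44 = 53.7, so **54 per group**.

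Variants that keep 5% and 80%:

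| Variant | n per group |
|---|---|
| Unrounded SD of 2.222 | 54 |
| t distribution (54.7) | 55 |
| One-sided 5% | 43 |
| Rank test, efficiency 0.955 | 57 |
| Rank test, efficiency 0.864 | 63 |

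None gives 70. What would come close is a changed input:

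- SD 2.53 in place of 2.22;
- d = 1.05 in place of 1.2;
- 90% power, which gives 71.9, so 72;
- one-sided 1%, which gives 69;
- a change-score SD with an assumed baseline-to-follow-up correlation of 0.35, which gives 70.

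The protocol states none of these.

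**The later steps**

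- From 70: 70/0.85 = 82.4 (82 stated), and 82 × 1.2 = 98.4 (about 100). These follow from 70 within rounding, so only the first link fails.
- From 54: 54/0.85 = 63.5, so 64, and 64 × 1.2 = 76.8, so 77 per group, about 154 in total.

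**Power on the stated inputs** (d = 1.2, SD 2.22, two-sided 5%, unadjusted two-sample t-test)

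| Per group | Power |
|---|---|
| 70 | 89% |
| 82 | 93% |
| 85 (100 less 15%) | 94% |
| 100 | 97% |

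With 85 per group, the difference detectable with 80% power is 0.96.

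**What the control arm does to d**

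d = 1.2 − (fall in mean control pain). The documents give no figure for that fall, so the values below are assumptions: 0%, 10%, 15% and 20% of the baseline mean of 3. SD is 2.22, with 85 evaluable per group.

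| Control fall | d | Power |
|---|---|---|
| 0 | 1.20 | 94% |
| 0.30 | 0.90 | 75% |
| 0.45 | 0.75 | 59% |
| 0.60 | 0.60 | 42% |

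By the protocol's formula, 80% power would need 96 evaluable per group for d = 0.90 and 215 for d = 0.60.

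**The case against.** **The slip is conservative and recruitment has closed.** This is true of the arithmetic. On the stated inputs, 70 per group has 89% power rather than 80%, and no participant, estimate or test is affected. It limits the consequence but does not make the printed figure right, and the question about d works the other way.

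**The output may be right and an input misprinted.** The 90%-power result of 72 is near 70, and a change-score SD with correlation 0.35 gives 70. Either is possible, but the documents support neither. What stands is that the authors should be free to identify the input they used, provided they print it.

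**The power figures are not those of the planned analysis.** This is fair. Statistical methods specifies negative binomial regression adjusted for baseline, whereas my figures follow the unadjusted two-mean method that the Sample size section itself uses. As a rough guide, linear adjustment with an assumed baseline-to-follow-up correlation of 0.3 to 0.5 raises power at 85 per group to 79–86% for d = 0.9, 63–72% for 0.75 and 45–53% for 0.6, and lowers the detectable difference to 0.92–0.83. Adjustment would also reduce the required n, so it cannot explain 70. Any restated power should be labelled as unadjusted.

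**A total of 200 is not an error.** Agreed. The last 20% is a discretionary allowance for subgroup work, and 154 only shows where the stated inputs lead.

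**The protocol defines d as a between-group difference, so 1.2 is simply the assumed effect.** It does, but the only justification offered for 1.2 is the intervention-arm forecast. The expected control-group catch-up at week 18, mentioned under Statistical methods, fits little control change before then, but it is not stated as a planning assumption.

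**Conclusion.** Both parts hold. The stated formula and inputs give 54 per group (55 by t-test); the stated 70 is 30% higher (70/54 = 1.30), and the 80% power attached to it is wrong for those inputs. This conclusion needs no assumption beyond the printed numbers.

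The value of d rests on an undeclared assumption of no change in the control arm. How much that matters depends on a control-arm change that the documents do not give. On the unadjusted calculation with 85 evaluable per arm, power falls below 80% once the true difference is smaller than 0.96, that is, once controls improve by more than 0.24 points (1.2 − 0.96). Baseline adjustment would soften this, by an amount that depends on a correlation that is not stated.

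The trial is not shown to be too small. Its stated justification is wrong as written and should be corrected before it is carried into the trial report.

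**What to change.** In the Sample size section:

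1. Correct 70 to 54 and carry it through (64 after dropout). If a different power, SD or correlation was actually used, print that input and show that it yields 70.
2. Keep 200 as the recruited number and restate what it provides, in terms such as: with 100 per group and 15% dropout, 85 evaluable per group give 94% power for a between-group difference of 1.2 (SD 2.22), or 80% power for 0.96, in an unadjusted two-sample comparison.
3. State that d = 1.2 assumes no mean change in the control arm, and give power at d = 0.9 (75%) and d = 0.75 (59%) on the same basis.
4. Record the correction by the route the protocol sets for modifications under Ethics and dissemination, including disclosure in the primary trial paper.

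The cost is a text correction. Recruitment closed on 2 October 2023, no participants need to be added, and the planned analysis does not change.

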The ZOLES trial is a pragmatic, outcome assessor blinded, randomised, controlled, superiority trial involving 200 recreational runners, randomised to receive either customised 3D-printed insoles (ZOLES) or to a "do-as-usual" control group. The study follows a robust protocol, ensuring adherence to established guidelines for clinical trials, and is based at St Mary's University, Twickenham, London. The primary outcome is change in running-related pain over a 10-week period, assessed using an 11-NRS pain scale. Secondary outcomes include overall pain and discomfort, running-related comfort, 5k-completion time, time-loss due to injuries, running exposure, and adherence to the intervention. A balanced-block randomisation process is stratified by sex and parkrun location, and an intention-to-treat analyses will be employed on all outcomes in the primary trial report. The trial includes a 52-week post-market surveillance to assess long-term effects of the customised insoles.

Discussion

The ZOLES trial aims to provide insights into real-world applicability and effectiveness of customised 3D-printed insoles in reducing running-related pain and enhancing overall running experience. Despite the limitation of a subjective primary outcome measure without participant blinding, the methodological rigor, including external outcome assessment and data handling, we anticipate results that are academically credible and applicable in real-world settings. The results of this trial may have important implications for runners, clinicians, and the sports footwear industry, as evidence for the use of individualised insoles to improve running experience and prevention of pain may become evident.

Trial registration

The trial was pre-registered at ClinicalTrials.gov with the trial identifier NCT06034210 on September 4, 2023, and publicly posted on September 13, 2023 (<https://clinicaltrials.gov/study/NCT06034210>).

Keywords

pain [MeSH]; running [MeSH]; foot orthoses [MeSH]; quality improvement [MeSH]; parkrun

Protocol version

Version 1, September 27, 2023.

Abbreviations¹

1

TPU: Thermoplastic Polyurethane
MCID: minimal clinical important difference
NRS: Numeric Rating Scale
GRoC: Global Rating of Change
CG: Control Group
IG: Intervention Group
ITT: Intention-to-treat
CONSORT: Consolidated standards of reporting trials
SPIRIT: Standard protocol items: Recommendations for interventional trials
TIDieR: Template for intervention description and replication

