No Intervention: “Do-as-usual” control group

Participants allocated to the control group are a "do-as-usual" comparator. This implies, that the participants may treat and prevent running-related pain and discomfort in any way they wish, except using the Zoles 3D-printed insoles.

Outcomes

Primary outcome

The primary outcome will be the change in running-related pain 10 weeks after baseline. Pain, although subjective, is a crucial determinant of runners' quality of life, performance, and continued participation in the activity [13]. For this trial, an 11-NRS pain scale will be utilized, ranging from 0 to 10 (0 = No pain at all, 10 = Worst pain imaginable) [48].

Baseline values for the primary outcome will be collected using online e-mail-distributed surveys via REDCap (Vanderbilt University, Nashville, TN, USA). Running-related pain data will be further collected at weekly intervals, with the focal analysis being between-group changes from baseline to the 10-week mark. The main outcome will be reported as the difference in mean change in running-related pain between the group using Zoles customised 3D-printed insoles and the "do-as-usual" control group, adjusting for values reported at baseline [49].

Secondary outcomes

The secondary outcomes include:

- **Global Rating of Change (GRoC) in overall daily pain and discomfort:** Participants will be asked to self-assess their perceived change in overall daily pain and discomfort relative to their state at the start of the study. They will use a 7-point scale, from -3 ("much worse") to 3 ("much better"), as indicated in the study by Bobos et al. [36] This outcome will be measured weekly until the 10-week mark, and again at the 18-week mark.
- **Running-related foot/footwear comfort:** The change in comfort from the start to the 10-week mark, relating specifically to running and footwear, will be captured using a numeric rating scale ranging from 0 (Extremely uncomfortable) to 10 (Extremely comfortable) based on the parameters defined by Menz & Bonnano [37]. This outcome will be measured at baseline with weekly follow-up measurements until the 10-week mark, and again at the 18-week mark.

- **5k-completion time:** The time taken by participants to complete their weekly 5 km parkrun will be recorded weekly, providing insights into any performance changes over the trial period.

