Specifically, the block randomisation will be stratified by sex and the specific parkrun location from which participants were recruited. This stratification ensures that each comparison group will have a representative mix of participants based on these two key variables, pre-hypothesised as potential confounders, allowing for a more controlled comparison of outcomes, and to improve external validity and generalisability of the results [51].

The process of generating the allocation sequence will be undertaken by an external who is not involved in any aspect of the trial to improve the integrity and credibility of the allocation process, as recommended [52]. The dataset provided for randomisation will only contain participant number, local parkrun location, and sex. The data will be initially separated by sex, and within each gender group, a stratification variable will be created based on local parkrun location. Block randomisation, with a block size of 4, will be conducted separately for males and females within each stratum (location) using a custom script developed in R. This approach ensures an equal or near-equal distribution of males and females within each treatment group across all locations. The randomisation process within each stratum will be automated through the script, and the resulting group assignments will be merged back into the original dataset. The R script used for the randomisation will be available as supplementary material to the primary trial report. Once the allocation sequence is generated, participants will be informed of their respective group assignments, either the intervention group (receiving the ZOLEs insoles) or the control group ("do-as-usual").

Blinding

Given the pragmatic nature of this trial, participants are not blinded to their group allocation. The absence of a sham insole for distribution means that participants will be aware of whether they are in the intervention group (receiving the ZOLEs insoles) or the control group ("do-as-usual"). Despite this, the allocation process remains concealed, ensuring that neither participants nor researchers are aware of the allocation sequence until the appropriate intervention shall be administered. This measure is in place to prevent any potential biases that might arise from foreknowledge of group assignments [53,54]. To further the study's integrity, we will use an external outcome assessor that is blinded to group assignments [55].

Procedures and data collection

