The trial will include prospective data collection using e-mail-distributed surveys via REDCap (Vanderbilt University, Nashville, TN, USA). Participants receive these surveys weekly for the initial 10 weeks, facilitating the collection of real-time data on their experience, pain levels, and the impact of the customised insoles for those in the intervention group. At the conclusion of this primary trial period (week 10), participants in the control group are provided with their customized insoles, marking the commencement of an additional 8-week observation period to compare intervention response between both groups (week 18). The final follow-up occurs at the 52-week mark, again via REDCap to provide insights on their long-term experiences, adverse effects, and the sustained impact of the Zoles insoles on their running-related pain and comfort.

Reminders will automatically be sent to participants at 24 hours and 48 hours after the original time of a follow-up questionnaire to participants failing to respond. Investigators will contact participants via telephone and SMS after another 24 hours if still not responding after receiving reminders to reduce the amount of missing data.

Data management

Every participant is assigned a unique identification number, ensuring their anonymity throughout the study in compliance with the General Data Protection Regulations (GDPR) under the Data Protection Act 2018.

Data collection, both at baseline and throughout the prospective stages, is facilitated via REDCap, a secure and robust online platform renowned for its data management capabilities [56]. This process is overseen from Department of Clinical Medicine at Aalborg University (DK-9220, Aalborg Øst, Denmark) by a dedicated data handler (CD), who remains blinded to group allocation. CD and FGL constitute the Data Monitoring Committee. A list of responding and non-responding participants is generated weekly, wherefrom a list of non-responding participants to contact is generated.

The Study Director (FGL) will maintain a secured key to the participants' identities, stored on a two-factor secured personal drive, ensuring the capability to identify and withdraw individual data if necessary.

All data is safeguarded within GDPR compliant two-factor and password-protected systems at St. Mary's University server, and on the REDCap online system. These measures ensure that the data remains inaccessible to unauthorized personnel, preserving confidentiality.

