Despite these challenges, the study's structure and methodology have been meticulously crafted to yield insights that are both scientifically rigorous and practically insightful, balancing between the ideal conditions for experimental control and the complexities of real-world application. Conversely, this study boasts several strengths that bolster its reliability and validity. The use of blinded group allocation sequence, external outcome assessors who are blinded to the group assignments, and an external data manager also blinded to group allocation ensures objectivity in data collection and analysis, minimizing bias. Furthermore, the recording of all outcomes in participants' natural environments, including baseline data, amplifies the real-world applicability of the findings. Participants are thus not influenced by the study personnel, ensuring the outcomes reflect the real-life effect of the intervention, enhancing the study's external validity. Additionally, the employment of a mobile scanning unit allows us to recruit participants from more distant parkrun locations, thus allowing for enrolment of participants who might not have the means to travel across London to partake in this study.

The intention to treat analysis in the primary study report ensures all participants are included in the final analysis, maintaining the randomisation benefits and offering a conservative estimate of the intervention's effectiveness. The step-wedge design addition enhances the study's robustness, allowing immediate verification of effectiveness by comparing the control group's response post-primary trial period to the intervention. The inclusion of a 52-week post-market surveillance further elevates the study's comprehensiveness, offering insights into the long-term effects and usability of the insoles.

Transparency is maintained through pre-registration of the study and the detailed description of the intervention using the TIDieR checklist [45], ensuring replicability and openness in reporting. The publication of this study protocol underscores the commitment to transparent and ethical research practices, contributing to the broader scientific discourse and public scrutiny.

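### The trial is labelled outcome-assessor blinded, but pain, GRoC and comfort are scored by participants who know their arm, and no masking of arm-revealing fields from the blinded data handler is described

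*Combined protocol and SAP*

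**What the plan says.** The abstract and the Trial design section describe a "pragmatic, outcome assessor blinded, randomised, controlled, superiority trial". The Blinding section says that "participants are not blinded to their group allocation" because there is no sham insole, and then adds, as a further protection, that "we will use an external outcome assessor that is blinded to group assignments".

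Under Primary outcome, "an 11-NRS pain scale will be utilized, ranging from 0 to 10". GRoC and footwear comfort are also rating scales (Secondary outcomes). Procedures and data collection says that follow-up data come from REDCap surveys e-mailed to participants, weekly for ten weeks.

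Data management says that the collection is overseen by a data handler "who remains blinded to group allocation". Strengths and limitations lists three things together: the blinded allocation sequence, the blinded external assessors and the blinded data manager. It says that this combination "ensures objectivity in data collection and analysis, minimizing bias".

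The abstract and Strengths and limitations both acknowledge that a subjective primary outcome is reported without participant blinding; the latter calls this a major limitation.

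**The concern.** Assessor blinding protects an outcome only where someone other than the unblinded participant judges or scores it. For a self-rated pain score, knowledge of the arm enters when the participant chooses the number. A blinded person further down the line cannot take it out. The plan nevertheless claims the protection by name and presents it as an offset: the abstract sets external outcome assessment against the admitted limitation, and Strengths and limitations extends the assurance to data collection.

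The second strand is the data handler. Blinded handling and analysis is a real safeguard that this trial could have, but it depends on the handler and the analyst not seeing fields that identify the arm. The plan asserts that blinding without saying how it is kept.

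At stake is whether the trial report describes its protections accurately, and whether the one kind of blinding still available after allocation is put into effect.

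**Working it through.** The plan has no figure on this point, so there is nothing to reproduce. The check is a comparison of sections.

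**Step 1. Who assesses each outcome?**

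| Outcome | Instrument | Who scores it | Knows the arm? |
|---|---|---|---|
| Running-related pain (primary) | 0 to 10 numeric scale | Participant, online survey | Yes |
| GRoC, daily pain and discomfort | 7-point scale, -3 to 3 | Participant, online survey | Yes |
| Foot/footwear comfort | 0 to 10 numeric scale | Participant, online survey | Yes |

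Sources: Primary outcome, Secondary outcomes, Procedures and data collection, Figure 3 and Blinding.

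**Step 2. What is left for the external assessor?** No section assigns a task. The outcome sections describe self-report, no adjudication of injuries is described, and Harms gives the evaluation of serious adverse events to the primary investigator. For the three outcomes above, the participant is therefore the assessor, and the assessor is not blinded.

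**Step 3. How much of the assurance survives?** Concealed allocation is described under Allocation and Blinding and can stand. Blinded handling and analysis can stand if it is put into practice. Objectivity in the collection of self-rated scores has no support.

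**Step 4. Can the data handler stay blinded?**
- The handler oversees REDCap collection at baseline and at follow-up (Data management).
- Use of the Zoles insoles in daily life and in running is an outcome over the ten weeks (Secondary outcomes). It is monitored weekly (Participant timeline) and marked from week 3 in Figure 3.
- Controls may not use these insoles in that period (control group description under Interventions) and receive theirs at week 10.
- Any reported use between weeks 3 and 10 therefore points to the intervention arm.
- Procedures and data collection also says that the weekly surveys gather "the impact of the customised insoles for those in the intervention group". This is narrative and does not prove a separate field, so the argument rests on adherence.
- No restriction of access to these fields is described. Statistical methods does not say who fits the primary model, or whether the arms are coded.

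**Step 5. Would withholding those fields hamper the primary analysis?** No. The planned model uses pain scores, arm and the baseline value. The imputation model uses preceding scores, age, sex, group and recruitment location. Neither needs adherence, and an A/B code serves for group.

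**The case against.** The strongest reply is that nothing is hidden. The abstract that carries the label also states the limitation, Blinding repeats it, and Strengths and limitations discusses Hawthorne and pleasing effects and explains why no sham was used. Open-label self-report is a reasoned pragmatic choice. All of that stands. A reader might infer that the plan conceals its lack of participant blinding, and the documents do not support that. But disclosure does not make the label true, because the abstract offers external assessment as the counterweight.

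A second reply is that the handler's blinding has not been shown to fail. This also stands. Access rights are not described, the weekly questionnaire appears only as an appendix title in the text available, and the one routine task spelled out is listing responders and non-responders. A reader might conclude that the handler is in fact unblinded; the supportable statement is that masking is not described. Nor could a handler who saw those fields change a score that the participant has already entered.

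A third reply is that the assurance also covers concealment and analysis, which have value. That is right, and only its reach into data collection should go.

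Two further inferences are tempting. One is to assume a between-arm reporting shift and quote an inflated false-positive rate. The documents give no such shift, and the result would describe any open-label trial of this size; none of the corrections here would alter it. The other is to test group by expectation in all participants. Expectation is not randomised, and the interaction could not separate biased reporting from a real response mediated by expectation.

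**Conclusion.** The plan states a property that it lacks for its primary outcome and for two secondary outcomes, GRoC and comfort. This affects the design label in two places, the promise under Blinding and one sentence in Strengths and limitations. That conclusion rests only on the plan's own description of who scores these outcomes and who knows the allocation.

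The handler strand is weaker. Weekly adherence data would reveal the arm if viewed, and no masking is described; whether they are viewed is unknown.

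No numerical bias follows from the documents, and none is claimed. How later readers or evidence syntheses would rate the trial is likewise a prediction that the documents cannot support. The choice of an open-label design is not faulted.

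**What to change.** 1. Describe the trial as open-label with participant-reported outcomes in the abstract and Trial design. Under Blinding, state role by role who is blinded, to what and until when. If the external assessor has a task, name it; if not, remove the role.
2. Limit the sentence in Strengths and limitations to allocation concealment and blinded data handling and analysis, and remove external outcome assessment as an offset in the abstract.
3. Give the analyst a restricted export with arms coded A/B and without adherence and insole-use fields until the primary model has been run.
4. Either mask those fields from the data handler or drop the statement that the handler is blinded.
5. Keep adverse-event data available for oversight. The handler is one of the two members of the Data Monitoring Committee (Data management), so withholding them would conflict with that role. Harms defines adverse events by allocation to the intervention, so these reports may themselves reveal the arm; the role-by-role statement should say so.

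The cost is a less favourable design label and the preparation of a restricted export. Design, outcomes and sample size are unchanged, and Ethics and dissemination already provides a route for recording protocol modifications.
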